6.8.5. Prohibited Medications and Procedures

The following medications are prohibited during the treatment and maintenance portions of the study (see also [Jakafi 2021](#) and [Jakavi 2022](#)):

- Any concurrent MF therapy other than that specified in the Protocol.
- Use of experimental drug therapy for MF or any other standard drug (except hydroxyurea) used for MF or another indication within 3 months of starting study drugs (ie, Day 1). Hydroxyurea used for MF or another indication must be discontinued 3 weeks prior to starting study drugs (ie, Day 1).
- Any investigational medication (for a non-MF indication) within 28 days or 5 half-lives, whichever is longer, before the first dose of study drug and at any time before complete withdrawal from the study.
- Use of potent inhibitors of CYP3A4 (eg, ketoconazole, clarithromycin, itraconazole, nefazodone or telithromycin, voriconazole or posaconazole); ketoconazole may be used with caution if other options are not available. Based on the low overall bioavailability of topical ketoconazole, there are no restrictions on topical ketoconazole in the study.
- Any live vaccine beginning 30 days before the first dose of study drug through the safety follow-up visit.

6.9. Treatment After Week 24

After 24 weeks, participants will enter the extension period of the study. Treatment will continue as long as the regimen is tolerated and the participant does not meet discontinuation criteria. Participants randomized to placebo will have the opportunity to cross over to receive parsacalisib (together with continued ruxolitinib) after the last randomized participant has reached Week 24 and all relevant data are entered and cleaned. These crossover participants may also continue as long as the regimen is tolerated and they do not meet discontinuation criteria. It is anticipated that individual participants will continue in the study for approximately 3 years. Extension studies may be implemented for continued access to study treatment.

7. DISCONTINUATION OF STUDY TREATMENTS AND PARTICIPANT WITHDRAWAL

7.1. Discontinuation of Study Treatment

7.1.1. Reasons for Discontinuation

Participants **must** be discontinued from study treatments (parsaclisib/matching placebo and ruxolitinib) for the following reasons:

- The participant becomes pregnant.
- Consent is withdrawn.
Note: Consent withdrawn means that the participant has explicitly indicated that he/she does not want to be followed any longer; in this case, no further data, except data in the public domain, may be solicited from or collected on the participant. Participants may choose to discontinue study treatment and remain in the study to be followed for progression and survival.
- Further participation would be injurious to the participant's health or well-being, in the investigator's medical judgment.
- Unacceptable toxicity, such as noted in Section 6.7.2.
- The study is terminated by the sponsor.
- The study is terminated by the local health authority, IRB, or IEC.

A participant **may** be discontinued from study drug and reference treatment as follows:

- If a participant is noncompliant with study procedures or study drug/treatment administration in the investigator's opinion, the sponsor should be consulted for instruction on handling the participant.

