6.7.2. Dose Decreases of Parsaclisib/Placebo for Toxicity

Parsaclisib or matching placebo should be interrupted/decreased first, with no change to the ruxolitinib dosage. Adjustments to ruxolitinib may be utilized if interruption/dose adjustment of parsaclisib or matching placebo does not lead to resolution or at least improvement of the AE within a 14-day period (see Section 6.7.7). Treatment with parsaclisib or matching placebo may be delayed up to 2 weeks (14 days) to allow for resolution of toxicity. Participants may resume

treatment if no medical condition or other circumstance exists that, in the opinion of the investigator, would make the participant unsuitable for further participation in the study. The treating investigator should contact the sponsor to discuss the case of any participant whose treatment has been delayed for more than 14 days before restarting treatment with piasclisib or matching placebo and/or ruxolitinib. Adverse events that have a clear alternative explanation or transient (≤ 72 hours) abnormal laboratory values without associated clinically significant signs or symptoms may be exempt from dose-reduction rules.

Table 11 shows dose-reduction and interruption guidelines for piasclisib and matching placebo. Because participants may enter the study with extensive pretreatment and/or severe bone marrow infiltration by the primary disease, these dose-reduction rules are provided as guidelines (see **Table 11**). **Individual decisions regarding dose reduction/interruption should be made using investigator clinical judgment and in consultation with the sponsor's medical monitor in those cases where the guidelines will not be followed, taking into account relatedness of the AE to piasclisib and the participant's underlying condition.** Available dose strengths for piasclisib/matching placebo are shown in **Table 12**.

Table 11: Guidelines for Interruption and Restarting of Piasclisib/Matching Placebo

Adverse Event	Action Taken
Chemistry	

 • AST and/or ALT $> 5.0 \times$ ULN (Grade 3). 	
Step 1: Interrupt piasclisib or matching placebo for up to 2 weeks (14 days) until the toxicity has resolved to \leq Grade 1 except by approval of the medical monitor.
 
Step 2: Restart piasclisib or matching placebo at the same dose. If assessed as related to piasclisib or matching placebo, restart piasclisib or matching placebo at the next lower dose; monitor as clinically indicated.

Hematology	

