6.7.6. Criteria for Permanent Discontinuation of Piasclisib/Matching Placebo

The occurrence of unacceptable toxicity not caused by the underlying disease will be presumed to be related to study drug treatment and will require that the study drug be permanently discontinued. Unacceptable toxicity is defined as follows:

- Occurrence of an AE that is related to treatment with the study drug that, in the judgment of the investigator or the sponsor's medical monitor, compromises the participant's ability to continue study-specific procedures or is considered to not be in the participant's best interest.
- An AE requiring more than 2 dose reductions.
- Persistent AE requiring a delay of therapy for more than 2 weeks (14 days) unless a greater delay has been approved by the sponsor.

See Section [7.1.2](#) for discontinuation procedures.

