6.7.7. Dose Decreases of Ruxolitinib for Safety

Dose modifications/interruptions of ruxolitinib because of toxicity are not required unless piasclisib modifications/interruptions have been first implemented for 14 days with no improvement in toxicity grade. Doses of ruxolitinib may be modified/interrupted earlier if the study investigator deems this necessary. Dose interruptions and modifications for ruxolitinib because of hematologic toxicity that continues after interruption of INCB050465 are shown in [Table 13](#).

Table 13: Dose Reductions/Interruptions and Restarts for Hematologic Toxicities That Persist for > 14 Days After Interruption of Parsaclisib

ANC ($\times 10^9/L$)			Platelet Count ($\times 10^9/L$)		Dose of Ruxolitinib
Value	CTCAE Grade		Value	CTCAE Grade	
0.5 to < 1.0	3	or	25 to < 40	Below UL of Grade 3	If Grade 3 cytopenia persists for > 14 days after interrupting parsaclisib/matching placebo or if the primary investigator deems that earlier interruption of ruxolitinib is necessary , then ruxolitinib will be interrupted until the toxicity is resolved to \leq Grade 1 or pretherapy baseline and then restarted at the current dose. If a Grade 3 event recurs and persists for > 14 days after interrupting parsaclisib/matching placebo or if the primary investigator deems that earlier interruption of ruxolitinib is necessary, then ruxolitinib will be interrupted and the restart dose (after recovery to \leq Grade 1 or pretherapy baseline) of ruxolitinib will be 1 dose level (5 mg BID less) lower than the dose that resulted in the cytopenia. A participant who was taking 5 mg BID will restart at 5 mg QD.
< 0.5	4	or	< 25	4	If Grade 4 thrombocytopenia or neutropenia occurs and persists for > 14 days after interrupting parsaclisib/matching placebo or if the primary investigator deems that earlier interruption of ruxolitinib is necessary , then ruxolitinib will be interrupted until toxicity is resolved to \leq Grade 1 or pretherapy baseline and the restart dose will be 1 dose level (5 mg BID less) lower than the dose that resulted in the cytopenia. A participant who was taking 5 mg BID ruxolitinib will restart at 5 mg QD.

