Neutropenic fever					If neutropenia (ANC < 1.0) persists for > 14 days after interrupting parsaclisib/matching placebo or if the primary investigator deems that earlier interruption of ruxolitinib is necessary, then ruxolitinib will be interrupted until recovery of ANC to $\geq 1.0 \times 10^9/L$ and the restart dose will be 1 dose level (5 mg BID less) lower than the dose that resulted in the cytopenia.

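### Protocol 7.1.1 requires ruxolitinib to stop for unacceptable toxicity, while the sections that define or list such toxicity stop only parsaclisib/placebo and Table 13 restarts ruxolitinib

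*Protocol*

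**What the plan says.** Protocol 7.1.1 lists the reasons for which participants must "be discontinued from study treatments (parsaclisib/matching placebo and ruxolitinib) for the following reasons". Both drugs are named. One reason is "Unacceptable toxicity, such as noted in Section 6.7.2".

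The term is defined only in Protocol 6.7.6, whose title and action cover parsaclisib/matching placebo. One of its three criteria is "Persistent AE requiring a delay of therapy for more than 2 weeks (14 days) unless a greater delay has been approved by the sponsor". Toxicity caused by the disease is outside the rule: "The occurrence of unacceptable toxicity not caused by the underlying disease will be presumed to be related to study drug treatment". For procedures, 6.7.6 sends the reader to 7.1.2.

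Protocol 6.7.2 does not define the term, but its Table 11 lists toxicities that end treatment permanently. Examples are pneumonitis or exfoliative dermatitis of Grade 2 or higher, intestinal perforation and confirmed PJP. Each of those entries names parsaclisib or matching placebo and not ruxolitinib.

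Protocol 6.7.7, Table 13, covers hematologic toxicity that outlasts the hold. Its first row opens with "If Grade 3 cytopenia persists for > 14 days after interrupting parsaclisib/matching placebo". Ruxolitinib is then interrupted until the toxicity has fallen to at most "Grade 1 or pretherapy baseline and then restarted at the current dose". For Grade 4 events and for neutropenic fever it is also interrupted, and "the restart dose will be 1 dose level (5 mg BID less) lower than the dose that resulted in the cytopenia". A recurrent Grade 3 event restarts one level lower as well. No row ends in a permanent stop of ruxolitinib.

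**The concern.** A site with a participant whose cytopenia has outlasted the hold can find two instructions for ruxolitinib. Section 7.1.1 ends it for good; Table 13 pauses it and brings it back. The drug in question is approved background therapy, so following the wrong section has a direct cost for the participant.

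It also changes what is collected. If both drugs stop, 7.1.2 treats the treatment portion as complete and 8.7 calls for an end-of-treatment visit, at which Table 3 marks no MRI. If ruxolitinib is restarted, the participant can stay on the schedule and reach the Week 24 scan and diary.

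**Working it through.** No power or sample-size figure is at issue. The check is a comparison of texts, followed by one piece of timing arithmetic.

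**Which drug does each section stop?**

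| Section | Trigger | Parsaclisib/placebo | Ruxolitinib |
|---|---|---|---|
| 7.1.1 | Unacceptable toxicity | Must stop | Must stop |
| 6.7.6 | Unacceptable toxicity, defined | Permanent stop | Not mentioned |
| 6.7.2, Table 11 permanent stops | Named toxicities | Permanent stop | Not mentioned |
| 6.7.7, Table 13 | Listed cytopenia more than 14 days after the hold | Already held | Interrupt, then restart |

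Section 7.1.1 is the only one that extends the stop to ruxolitinib. Section 6.7.6 alone is compatible with Table 13.

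**Does a Table 13 event meet the 6.7.6 definition?** Table 11 holds parsaclisib/placebo for cytopenia for up to 14 days, until recovery to Grade 1 or pretherapy baseline. A cytopenia still at Table 13 severity after 14 days has therefore required a delay of more than 14 days. It meets the definition unless the sponsor approved a longer delay or the underlying disease is the cause.

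**Test case.** Take a Grade 3 neutropenia that is a worsening from baseline and not due to disease. Parsaclisib/placebo is held on day 0, the event is still Grade 3 on day 15, and no longer delay is approved.

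1. Under 6.7.6 this is unacceptable toxicity, so parsaclisib/placebo stops permanently.
2. Under 7.1.1 unacceptable toxicity means both drugs must stop.
3. Under Table 13 ruxolitinib is interrupted and, for a first Grade 3 event, restarted at the current dose after recovery.

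Steps 2 and 3 cannot both be followed, and no text ranks one section above the other.

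**When could it fall before the Week 24 scan?** Table 5 schedules hematology at Weeks 2, 4, 6, 8, 10, 12, 16, 20 and 24. A hold opened at Week d reaches its limit on Day 7d + 14, and Week 24 is Day 168. The days left are 168 − (7d + 14) = 154 − 7d:

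| Week d | 2 | 4 | 6 | 8 | 10 | 12 | 16 | 20 | 24 |
|---|---|---|---|---|---|---|---|---|---|
| Days left | 140 | 126 | 112 | 98 | 84 | 70 | 42 | 14 | −14 |

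So 8 of the 9 draws leave between 2 weeks (14/7) and 20 weeks (140/7) before the scan. This shows where the case can arise, not how often it does.

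**The case against.** The best defence reads 7.1.1 through its own pointer. Section 6.7.2 contains Table 11, whose permanent stops are a sensible target for the reference, and Table 11's cytopenia rows all end in a restart. On that reading 7.1.1 never reaches the cytopenias of Table 13. Part of this stands: the pointer to 6.7.2 is not an error and should be kept. It does not remove the problem. The reference gives examples only, the defined term is in 6.7.6, and 6.7.6 leads back into the discontinuation procedures of 7.1.2. The Table 11 stops also name only parsaclisib/placebo, so 7.1.1 goes too far on ruxolitinib even there.

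Second, sponsor involvement is the expected path at 14 days: "The treating investigator should contact the sponsor to discuss the case of any participant whose treatment has been delayed for more than 14 days". That passage also foresees restarting ruxolitinib. This stands, and it makes the case narrow. But contact is not approval. If the sponsor does not approve a longer delay, parsaclisib/placebo stops under 6.7.6 and 7.1.1 then takes ruxolitinib with it.

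Third, Table 13 has another trigger: the investigator may interrupt ruxolitinib earlier. No conflict need arise in those cases.

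Fourth, the intent is fairly clear. Sections 6.7.2 and 6.7.7 adjust ruxolitinib rather than end it. That stands, and it identifies 7.1.1 as the text to correct.

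**Conclusion.** The wording of 7.1.1 is wrong, at low priority. It requires ruxolitinib to stop where 6.7.6 and the Table 11 permanent stops end only parsaclisib/placebo. It directly contradicts Table 13 for a Grade 3 or 4 neutropenia, a platelet count below 40 × 10^9/L, or neutropenic fever that is not due to underlying disease and outlasts the 14-day hold without an approved longer delay. This rests on taking unacceptable toxicity in 7.1.1 to carry its 6.7.6 meaning, the only definition given.

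A reader might infer a loss of power or a biased primary result. The documents do not support that, because they give no rate of such stops. One participant is 1/220 = 0.45 percentage points of an arm. For scale, Protocol Table 19 puts the final threshold at response rates of 50.5% (normal platelets) and 23.4% (low), against planned rates of 58.2% and 29.4%. With all participants in the normal stratum the gap is 220 × (0.582 − 0.505) = 16.9 responders. With an assumed 30% low-platelet share it is 220 × (0.70 × 0.077 + 0.30 × 0.060) = 15.8. Nothing in the documents suggests that many.

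A reader might also infer that the choice of section decides responder status. That is not shown either. SAP 7.3.1 and 7.4.2.2 count anyone who stopped treatment before Week 24 as a nonresponder without naming the drug. If a permanent parsaclisib/placebo stop counts, the participant is a nonresponder with or without a scan. That SAP ambiguity is a separate matter and adds no weight here.

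What is shown is the effect on the individual participant's background therapy and on whether Week 24 data exist.

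**What to change.** (a) In 7.1.1, keep the reference to 6.7.2 and replace the toxicity bullet with wording such as: *Unacceptable toxicity as noted in Section 6.7.2 (Table 11) or defined in Section 6.7.6: parsaclisib/matching placebo must be permanently discontinued. Ruxolitinib is handled per Section 6.7.7/Table 13 for hematologic toxicity, and otherwise may continue unless the investigator judges further participation injurious (see the bullet above).* This keeps Table 11's named stops in view and uses the existing harm criterion for nonhematologic toxicity.

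(b) In 7.1.2, align with 8.7. The end-of-treatment visit applies only when both drugs have stopped. A participant who stops only parsaclisib/placebo keeps the scheduled visits, the Week 12 and Week 24 MRI, and the diary through Week 24.

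The cost is one bullet and one sentence, with no visits or scans beyond the existing schedule. The downside is procedural: under Protocol 11.1 an amendment needs health-authority and IRB/IEC approval, so these edits should be bundled with the next one. Which drug's stop counts as discontinuing treatment in the SAP should be raised separately.

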7.1.2. Discontinuation Procedures

The decision to discontinue study treatment and reference treatment will not constitute study withdrawal or study completion. In the event that the decision is made to discontinue study treatment and reference treatment, the treatment portion will be considered complete and the follow-up part of the study will begin.

If a participant is discontinued from study treatment:

- The study monitor or sponsor must be notified.
- The reason(s) for discontinuation must be documented in the participant's medical record and the primary reason for discontinuation must be included in the eCRF.
- The EOT visit should be performed and date recorded.
- The last date of the last dose of study drug/reference treatment will be recorded in the eCRF.
- The status of the participant should be updated to EOT in the IXRS.

- Participants must be followed for safety until the time of the follow-up visit or until study drug/reference treatment–related toxicities resolve, return to baseline, or are deemed irreversible, whichever is longest.
- Participants will be followed for subsequent MF treatment regimens and survival via periodic telephone contact. Results of these contacts will be recorded in the eCRF.

If the participant discontinues study treatment/reference treatment and actively withdraws consent for collection of follow-up data (safety follow-up or disease assessment), then no additional data collection should occur; however, participants will have the option of withdrawing consent for study treatment/reference treatment and further assessments but allowing survival follow-up.

7.2. Participant Withdrawal From the Study

A participant may withdraw from the study at any time at his/her own request, or may be withdrawn at any time at the discretion of the investigator for safety, behavioral, compliance, or administrative reasons.

If the participant withdraws consent for disclosure of future information, the sponsor may retain and continue to use any data collected before such a withdrawal of consent.

If a participant withdraws from the study, he/she may request destruction of any samples taken and not tested, and the investigator must document this in the site study records.

See [Table 3](#) and [Table 5](#) for data to be collected at the time of study withdrawal and follow-up and for any further evaluations that need to be completed.

7.3. Lost to Follow-Up

A participant will be considered lost to follow-up if he/she repeatedly fails to return for scheduled visits and is unable to be contacted by the study site.

The following actions must be taken if a participant fails to return to the clinic for a required study visit:

- The site must attempt to contact the participant and reschedule the missed visit as soon as possible and counsel the participant on the importance of maintaining the assigned visit schedule and ascertain whether or not the participant wishes to and/or should continue in the study.
- Before a participant is deemed lost to follow-up, the investigator or designee must make every effort to regain contact with the participant (where possible, 3 telephone calls and, if necessary, a certified letter to the participant's last known mailing address or local equivalent methods). These contact attempts should be documented in the participant's medical record.
- Should the participant continue to be unreachable, he/she will be considered to have withdrawn from the study.

8. STUDY ASSESSMENTS AND PROCEDURES

All assessments mandated throughout the study must be performed on a calendar schedule; delays in treatment administration will not delay performance of study visits, laboratory-only visits, or assessments (except [REDACTED] because participant accidentally took the study drugs in the morning of the study visit at Week 2 or 4; see Section 8.4.1).

8.1. Administrative and General Procedures

8.1.1. Informed Consent Process

- The investigator or his/her representative will explain the nature of the study to the participant or his/her legally authorized representative and answer all questions regarding the study.
 - Informed consent must be obtained before any study-related procedures are conducted, unless otherwise specified by the Protocol.
 - Informed consent must be obtained using the IRB/IEC-approved version in a language that is native and understandable to the participant. A template will be provided by the sponsor or its designee. The sponsor or its designee must review and acknowledge the site-specific changes to the ICF template. The ICF must include a statement that the sponsor or its designee and regulatory authorities have direct access to participant records.
 - The ICF must contain all required elements and describe the nature, scope, and possible consequences of the study in a form understandable to the study participant.
- Participants must be informed that their participation is voluntary. Participants or their legally authorized representative will be required to sign a statement of informed consent that meets the applicable requirements and regulations for the country(ies) in which the study is being conducted as well as the IRB/IEC or study center.
- The participant must be informed that his/her personal study-related data will be used by the sponsor in accordance with local data protection laws. The level of disclosure must also be explained to the participant.
- The participant must be informed that his/her medical records may be examined by Clinical Quality Assurance auditors or other authorized personnel appointed by the sponsor, by appropriate IRB/IEC members, and by inspectors from regulatory authorities.
- The medical record must include a statement that written informed consent was obtained before the participant was enrolled in the study and the date the written consent was obtained. The authorized person obtaining the informed consent must also sign the ICF.
- Participants must provide consent to the most current version of the ICF during their participation in the study.

- A copy of the ICF(s) must be provided to the participant or the participant's legally authorized representative.
- Participants who are rescreened are required to sign a new ICF.

